1. Disease activity data (ACR20/50/70, DAS28, CDAI, SDAI, and blood sampling for ESR), blood for clinical laboratory tests, blood for biomarker assessments, and blood for possible future PD assessments will be collected prior to dosing on Day 1. Blood sampling for ESR will be collected and assessed at local laboratory.
2. Disease activity data (ACR20/50/70, DAS28, CDAI, SDAI, and blood sampling for ESR), blood for biomarker assessments, and blood for possible future PD assessments will be collected prior to dosing on Day 7 only. Blood sampling for ESR will be collected and assessed at local laboratory.
3. A full physical examination will be performed at the Screening Visit, Day 14, and Early termination visit; a brief physical will be performed on Days -1 and 10.
4. Blood for clinical laboratory tests will be withdrawn once on Days 4 and 7.
5. Vital signs will be collected at pre-dose and 1, 2, 4, 8, and 12 hours after dosing on Day 1.
6. 12-lead ECG will be conducted before blood sampling.
7. 12-lead ECG will be repeated once for eligibility confirmation at Screening and Day -1.
8. 12-lead ECG will be recorded at baseline and at 1, 2, 4, and 8 hours after dosing on Days 1 and 7.
9. Starting 2 hours prior to dosing and until 12 hours after dosing on Days 1 and 7.
10. Blood for PK sample analysis to determine parent and its metabolite concentrations and for possible future metabolite assessments will be sampled at pre-dose and 0.25, 0.5, 1, 1.5, 2, 3, 4, 6, 8, 12, 16, and 24 hours (pre-dose of Day 2) after dosing on Day 1, pre-dose on Days 3, 4, 5, 6, and on 7 at pre-dose and 0.25, 0.5, 1, 1.5, 2, 3, 4, 6, 8, 12, 16, 24, 48, and 72 hours after dosing on Day 7 (the sampling time points may be adjusted based on the PK results obtained from the previous parts or cohorts). The last dose will be administered on Day 7.
11. Urine for PK sample analysis will be collected at 0 (pre-dose) to 6, 6 to 12, and 12 to 24 hours after dosing on Day 1, and from 0 (pre-dose) to 6, 6 to 12, 12 to 24, 24 to 48, and 48 to 72 hours after dosing on Day 7. Urine collection intervals may be adjusted based on the PK results obtained from the previous parts or cohorts, e.g., if plasma PK sampling times are adjusted, the urine sampling times will be updated.
12. Sample will be obtained only from patients that consent to pharmacogenomics sampling.

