Dose escalation will only be allowed after blinded assessment of all safety, tolerability, and PK data up to Day 10 from each previous cohort evaluated by Investigators, Medical Monitor, and Sponsor representatives during the Safety Review Committee (SRC) meeting.

All patients (including patients who terminate the study early) will return to the site 13 days after the first TCK-276 or TCK-276 matching placebo administration for follow-up procedures and for the end of treatment examination.

Duration of patient participation from the Screening Visit to the end of treatment examination will be approximately 42 days. This includes 27 days for the Screening period, 11 days for the in-house Treatment period (patients will be confined from the morning of Day -1 until all safety assessments have been completed on Day 10), and 4 days after the end of the Treatment period, for the Follow-up/EOT Visit.

If the Investigator, the Sponsor, or the Medical Monitor becomes aware of conditions or events that suggest a possible hazard to patients if the clinical study continues, the clinical study may be terminated after appropriate consultation between the involved parties. The clinical study may also be terminated at the Sponsor's discretion in the absence of such a finding.

Figure 4-1 Study Flow Chart – Multiple Ascending Dose Design

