7.1.1 Overall Study Stopping Criteria

The study will be stopped if any of the following occur and are thought to be at least possibly related to study intervention agreed upon by the SRC:

- Two patients develop the same Grade 3 AE (grading is based on the Common Terminology Criteria for Adverse Events [CTCAE] version 5.0).
- One patient develops \geq Grade 4 AE (CTCAE version 5.0).
- Death of a patient at any time.

If any of the following scenarios occur within a cohort with reasonable possibility of a causal relationship with study drug, dosing will be stopped, and further dosing will not be initiated.

- One or more patients experience increased alanine ALT or AST $> 3 \times$ ULN with total bilirubin (TBL) $> 2 \times$ ULN or increased AST $> 3 \times$ ULN accompanied by alkaline phosphatase (ALP) $> 1.5 \times$ ULN.
- One or more patients experience a decrease of absolute neutrophil count less than 1,000/mm³ or white blood cell (WBC) less than $2.5 \times 10^3/\mu\text{L}$ or platelet count less than 75,000/ μL .
- One or more patients have an increase of more than 60 ms in QTcF compared to the baseline QTcF (baseline QTcF = value obtained on Day 1 at pre-dose in the treatment period) or QTcF > 500 ms or other clinically significant conduction disturbance or arrhythmia. All ECGs for this determination must be performed under strict resting conditions.
- Two or more patients, who receive study intervention, have tachycardia defined as resting supine heart rate > 125 beats per minute (bpm) persisting for at least 10 minutes.
- Two or more patients, who receive study intervention, have symptomatic bradycardia defined as resting supine heart rate < 40 bpm accompanied with symptoms of bradycardia while awake persisting for at least 10 minutes.
- Two or more patients, who receive study intervention, develop hypertension defined as an increase in resting supine systolic blood pressure (BP) > 40 mmHg to above a reading of 180 mmHg and persisting for at least 10 minutes.

If the criteria were met, the SRC will carefully review the totality of data, considering moderate non-serious AEs at least possibly related to the study intervention administration in unblinded

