7.2 Patient Discontinuation/Withdrawal from the Study

A patient may withdraw from the study at any time at their own request or may be withdrawn at any time at the discretion of the Investigator for safety, behavioral, or compliance reasons. The patient will be permanently discontinued from the study intervention and the study at that time.

If the patient withdraws consent for disclosure of future information, the Sponsor may retain and continue to use any data collected before such a withdrawal of consent.

If a patient withdraws from the study, he/she may request destruction of any samples taken and not tested, and the Investigator must document this in the site study records.

At the time of discontinuing from the study, if possible, an early discontinuation visit should be conducted, as shown in the SoA ([Table 1-1](#)). Refer to the SoA for data to be collected at the time of study discontinuation and follow-up and for any further evaluations that need to be completed.

In addition to the stopping rules described in Section [7.1.1](#), a patient will be withdrawn by the Investigator or designee from the study and not be allowed to continue with the study if any of the following criteria are fulfilled:

- Any patient who develops an AE \geq Grade 3 (CTCAE version 5.0).

- Patient will be discontinued from further dosing if following toxicities are observed:
 - Hematologic: Neutropenia, absolute neutrophil count < 1000/mm³, hemoglobin < 9 g/dL, white blood cell < 2.5 × 10³/µL
 - Renal: serum creatinine > 3 × ULN
 - Hepatic: bilirubin elevation > 2 × ULN; AST or ALT elevation > 3.0 × ULN
 - QTcF prolongation: mean QTcF ≥ 500 ms or change from the nearest baseline > 60 ms
 - ECG abnormalities including ventricular tachycardia or ventricular fibrillation, complete heart block (Grade III atrioventricular block) or second degree atrioventricular block Mobitz type II
 - Hypertension: resting systolic BP ≥ 180 mmHg and ≤ 80 mmHg diastolic BP
Hypotension: resting systolic BP ≥ 110 mmHg and ≤ 40 mmHg diastolic BP
 - Pulse (resting) < 35 or > 110 bpm
- A patient may withdraw from the study at any time at his/her own request or may be withdrawn at any time at the discretion of the Investigator for safety, behavioral or administrative reasons.
- If the patient withdraws consent for disclosure of future information, the Sponsor may retain and continue to use any data collected before such a withdrawal of consent.

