7.3 Lost to Follow-Up

A patient will be considered lost to follow-up if they repeatedly fail to return for scheduled visits and are unable to be contacted by the study site.

The following actions must be taken if a patient fails to return to the clinic for a required study visit:

- a. The site must attempt to contact the patient and reschedule the missed visit as soon as possible (and within the visit window, where one is defined), counsel the patient on the importance of maintaining the assigned visit schedule, and ascertain whether the patient wishes to and/or should continue in the study.
- b. In cases in which the patient is deemed lost to follow-up, the Investigator or designee must make every effort to regain contact with the patient (where possible, 3 telephone calls and, if necessary, a certified letter to the patient's last known mailing address or local equivalent methods). These contact attempts should be documented in the patient's medical record/case report form (CRF).

- c. Should the patient continue to be unreachable, he/she will be considered to have withdrawn from the study.
- d. Site personnel, or an independent third party, will attempt to collect the vital status of the patient within legal and ethical boundaries for all patients randomized, including those who did not get study intervention. Public sources may be searched for vital status information. If vital status is determined as deceased, this will be documented and the patient will not be considered lost to follow-up. Sponsor personnel will not be involved in any attempts to collect vital status information.

8 Study Assessments and Procedures

Study procedures and their timing are summarized in the SoA ([Table 1-1](#)). Protocol waivers or exemptions are not allowed.

A Safety Management Plan (SMP) will be signed between the Sponsor and [REDACTED].

Immediate safety concerns should be discussed with the Sponsor immediately upon occurrence or awareness to determine if the patient should continue or discontinue study intervention.

Adherence to the study design requirements, including those specified in the SoA, is essential and required for study conduct.

All screening evaluations must be completed and reviewed to confirm that potential patients meet all eligibility criteria. The Investigator will maintain a screening log to record details of all patients screened and to confirm eligibility or record reasons for screening failure, as applicable.

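### Section 7.2 stops an individual for low pulse only below 35 bpm, so a first symptomatic patient at 35 to 39 bpm meets no numeric rule stopping their own dosing

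*Protocol*

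**What the plan says.** Protocol Section 7.2 lists toxicities at which a patient must receive no further doses. Its only heart-rate entry is "Pulse (resting) < 35 or > 110 bpm". That entry has no condition on symptoms, posture, wakefulness or duration.

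Protocol Section 7.1.1 holds the cohort-level criteria, which apply when a causal link with study drug is reasonably possible. The bradycardia criterion begins "Two or more patients, who receive study intervention, have symptomatic bradycardia" and is defined as "resting supine heart rate < 40 bpm accompanied with symptoms of bradycardia while awake persisting for at least 10 minutes". One patient does not trigger it. A different bullet, mainly about QTcF, does act on a single patient and closes with "other clinically significant conduction disturbance or arrhythmia".

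Three other provisions bear on the same patient:

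- Section 7.2 withdraws anyone with an AE of Grade 3 or higher.
- Section 7.2 stops dosing for ECG abnormalities, naming ventricular tachycardia or fibrillation, complete heart block and Mobitz II block as inclusions rather than as a closed list.
- Section 7.2 allows withdrawal at the Investigator's discretion for safety. The opening of Section 8 adds that "Immediate safety concerns should be discussed with the Sponsor immediately upon occurrence or awareness", so that continuation can be decided.

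The SAP sets no individual stopping rule. Its Section 4.13.10 describes only the Safety Review Committee's review.

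**The concern.** For a criterion that needs two patients, the individual limit is what protects the first one. On the fast side this works: 7.2 stops a patient above 110 bpm, well before 7.1.1 starts counting above 125 bpm. On the slow side the order is reversed. A brief, symptom-free reading of 34 bpm is a mandatory stop, while ten minutes of symptomatic 38 bpm is not, although the protocol itself counts the second event as a signal against the cohort.

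At stake is whether a patient with sustained symptomatic bradycardia receives the next daily dose. In a multi-center study, the same event could lead to a stop at one site and re-dosing at another, depending on how each site grades or classifies it.

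**Working it through.** The plan states no figure to reproduce. The check applies the two rules side by side.

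**1. Rules applied to whole-number heart rates.** Inputs: 7.2 (below 35 or above 110 bpm) and 7.1.1 (below 40 bpm with symptoms, above 125 bpm, each for at least 10 minutes).

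| Heart rate (bpm) | 7.2 stops this patient | 7.1.1 counts this patient |
|---|---|---|
| 34 | yes | yes, if symptomatic |
| 35, 36, 37, 38, 39 | no | yes, if symptomatic |
| 40 and 110 | no | no |
| 111 and 125 | yes | no |
| 126 | yes | yes |

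The uncovered band is 40 − 35 = 5 bpm.

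**2. Other parameters.**

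- Neutrophils and white cells have the same limits in both sections.
- For transaminases, 7.2 acts on ALT or AST above 3 × ULN alone. 7.1.1 also requires raised bilirubin or alkaline phosphatase.
- QTcF limits are close but not identically defined. 7.2 uses a mean QTcF and the nearest baseline; 7.1.1 uses the Day 1 pre-dose baseline.
- Platelets have a limit only in 7.1.1, but one patient is enough there.
- Hypertension is also mismatched. As printed, 7.2 needs systolic at or above 180 mmHg together with diastolic at or below 80 mmHg. A first patient who rises by more than 40 mmHg to 190/100 for at least 10 minutes is counted by 7.1.1 and missed by the 7.2 line.

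**3. What can stop the first patient at 35 to 39 bpm.**

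- *Grade 3 or higher:* Appendix 3 (10.3.3) separates Grade 2, moderate, from Grade 3, severe or medically significant. A symptomatic episode that resolves could be graded either way.
- *ECG line in 7.2:* the list is open, but slow sinus rate is not named.
- *One-patient clause in 7.1.1:* the site must class the slow rate as a clinically significant arrhythmia with a possible causal link. Doing so stops dosing for the cohort on one case, which sits awkwardly beside a separate two-patient bradycardia criterion.
- *Investigator discretion and Sponsor discussion:* neither requires a stop.

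**4. Doses exposed.** With dosing on Days 1 to 7, an event on Day d leaves 7 − d doses: 6 after Day 1, 5 after Day 2, down to 0 after Day 7. Of the 6 after Day 1, the five on Days 2 to 6 have vital signs scheduled without stated post-dose times, and no scheduled telemetry or timed post-dose ECG. The schedule's footnotes read "Vital signs will be collected at pre-dose and 1, 2, 4, 8, and 12 hours after dosing on Day 1" and "12-lead ECG will be recorded at baseline and at 1, 2, 4, and 8 hours after dosing on Days 1 and 7", and scheduled telemetry is also limited to Days 1 and 7.

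**5. How often the two-patient rule would leave a lone case.** The documents give no event rate, so p below is an assumption. Events are taken as independent among 6 active patients, with an event meaning the full 7.1.1 bradycardia definition.

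P(exactly one) = 6p(1 − p)^5; P(two or more) = 1 − (1 − p)^6 − 6p(1 − p)^5. The last column is the first probability divided by the sum of the two.

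| Assumed p | Exactly one | Two or more | Lone case, given any |
|---|---|---|---|
| 0.05 | 0.232 | 0.033 | 0.232/0.265 = 0.88 |
| 0.10 | 0.354 | 0.114 | 0.354/0.468 = 0.76 |
| 0.20 | 0.393 | 0.345 | 0.393/0.738 = 0.53 |
| 0.30 | 0.303 | 0.580 | 0.303/0.883 = 0.34 |

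The rarer the event, the more the individual rule matters, because a first case is then usually the only case. These figures include rates below 35 bpm, which 7.2 already covers, so they overstate the gap itself.

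**The case against.** **The rules measure different things.** The 7.2 entry is an unconditional reading; the 7.1.1 entry needs posture, wakefulness, symptoms and duration. A lower number for the unconditional rule is a defensible clinical choice. This stands as a reason to keep 35 bpm for any patient. It does not explain why the symptomatic case has no individual line.

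**Backstops exist, and some are mandatory once invoked.** A Grade 3 grading or the 7.1.1 arrhythmia clause compels a stop. A reader might infer that nothing can stop this patient; the documents do not support that. What remains is that every route turns on how the event is graded or classified.

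**Low pulse is not unique.** A reader might take it as the one departure from an otherwise consistent scheme. The hypertension line shows otherwise.

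**Harm needs a chain of events.** The patient must be symptomatic, awake and at 35 to 39 bpm for ten minutes, must be the first in the cohort, and must then be re-dosed despite the safeguards. Section 4.1 says "patients will be confined from the morning of Day -1 until all safety assessments have been completed on Day 10", and Section 8.3.4 requires ECG and continuous monitoring to be repeated hourly after a significant telemetry change until resolution or stability. Exclusion criteria 13, 14 and 34 remove arrhythmia, heart block, cardiopathy and a history of fainting. Safety pharmacology (2.2.1) found no untoward effects, and the single-dose study (2.2.2) reported no drug-related safety signals up to 185 mg. This stands, and it limits the weight of the point.

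**The change does not remove judgement.** The Investigator must still attribute symptoms to bradycardia. That is true, but the judgement becomes narrower: one defined question instead of a choice among several routes.

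**Conclusion.** The gap is real on the text and modest in practice. A first patient with sustained symptomatic heart rate of 35 to 39 bpm counts toward the two-patient stop in 7.1.1 and meets no numeric rule in 7.2 that ends their own dosing. Stopping that patient is possible but depends on judgement, and between 0 and 6 doses could follow, according to the day of the event.

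The conclusion rests only on the two printed thresholds and the two-patient condition. It assumes no event rate; the rates in the working are illustrative. A reader might infer that bradycardia is an expected effect of TCK-276; the documents list no such signal. A reader might also take the thinner scheduled monitoring on Days 2 to 6 as part of the fault. It describes the setting for re-dosing, but it is a matter for the assessment schedule, and changing the threshold would not alter it.

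This is a cheap improvement to an incomplete stopping rule, not a flaw that puts the study's conclusions in doubt.

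**What to change.** Extend the pulse line in Protocol Section 7.2 so that it also stops a patient with symptomatic resting supine heart rate below 40 bpm, while awake, lasting at least 10 minutes. Keep the limit of 35 bpm regardless of symptoms, and leave symptom-free rates of 35 to 39 bpm to the existing judgement routes. Every patient counted by the 7.1.1 bradycardia criterion would then already have stopped dosing, as happens with tachycardia.

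The cost is one entry in a protocol amendment, using data already collected, and possibly a few more individual discontinuations. Section 7.2 says patients withdrawn for drug-related AEs are generally not replaced. For related events on active drug, the addition is at most 2 − 1 = 1 per cohort, because a second such patient meets the 7.1.1 rule anyway. With no other dropouts that leaves 6 − 1 = 5 active patients and 8 − 1 = 7 in total, above the escalation minimums of 4 and 6 in Section 7.1.2. The bound is conditional: the new entry has no causality test, so placebo or unrelated events could add more.

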7.3 Lost to Follow-Up

A patient will be considered lost to follow-up if they repeatedly fail to return for scheduled visits and are unable to be contacted by the study site.

The following actions must be taken if a patient fails to return to the clinic for a required study visit:

- a. The site must attempt to contact the patient and reschedule the missed visit as soon as possible (and within the visit window, where one is defined), counsel the patient on the importance of maintaining the assigned visit schedule, and ascertain whether the patient wishes to and/or should continue in the study.
- b. In cases in which the patient is deemed lost to follow-up, the Investigator or designee must make every effort to regain contact with the patient (where possible, 3 telephone calls and, if necessary, a certified letter to the patient's last known mailing address or local equivalent methods). These contact attempts should be documented in the patient's medical record/case report form (CRF).

- c. Should the patient continue to be unreachable, he/she will be considered to have withdrawn from the study.
- d. Site personnel, or an independent third party, will attempt to collect the vital status of the patient within legal and ethical boundaries for all patients randomized, including those who did not get study intervention. Public sources may be searched for vital status information. If vital status is determined as deceased, this will be documented and the patient will not be considered lost to follow-up. Sponsor personnel will not be involved in any attempts to collect vital status information.

8 Study Assessments and Procedures

Study procedures and their timing are summarized in the SoA ([Table 1-1](#)). Protocol waivers or exemptions are not allowed.

A Safety Management Plan (SMP) will be signed between the Sponsor and [REDACTED].

Immediate safety concerns should be discussed with the Sponsor immediately upon occurrence or awareness to determine if the patient should continue or discontinue study intervention.

Adherence to the study design requirements, including those specified in the SoA, is essential and required for study conduct.

All screening evaluations must be completed and reviewed to confirm that potential patients meet all eligibility criteria. The Investigator will maintain a screening log to record details of all patients screened and to confirm eligibility or record reasons for screening failure, as applicable.

Procedures conducted as part of the patient's routine clinical management (e.g., blood count) and obtained before signing of the ICF may be used for screening or baseline purposes provided the procedures met the protocol-specified criteria and were performed within the timeframe defined in the SoA.

Safety/laboratory/analyte results that could unblind the study will not be reported to investigative sites or other blinded personnel until the study has been unblinded.

The maximum amount of blood collected from each patient over the duration of the study, including any extra assessments that may be required, will not exceed 600 mL

Blood samples of approximately 520 mL will be collected for measurement of blood concentrations of TCK-276 and TEI-W00595 as specified in the SoA ([Table 1-1](#)) throughout the study period. A maximum of 30 samples may be collected at additional timepoints during the

study if warranted and agreed upon between the Investigator and the Sponsor. The timing of sampling may be altered during the course of the study based on newly available data (e.g., to obtain data closer to the time of peak plasma concentrations) to ensure appropriate monitoring. Instructions for the collection and handling of biological samples will be provided by the Sponsor. The actual date and time (24-hour clock time) of each sample will be recorded.

Repeat or unscheduled samples may be taken for safety reasons or for technical issues with the samples.

